5.1 General Design Description

We propose the following study in patients who have been evaluated for primary nocturnal enuresis in our Yale New Haven Clinics.

- All patients to be evaluated for nocturnal enuresis will undergo standard evaluation and initial treatment for nocturnal enuresis which includes:
 - Assessment Of Bowel Habits,
 - Fill Out A Questionnaire To Evaluate For Voiding Dysfunction
 - Treatment with routine bedwetting protocol of:
 1. Stopping drinks 1 HR before bedtime, meals at least 3 hrs before bedtime, eliminating milk and ice cream from dinner and on, making sure that bowel movements are occurring 4 times per week and treating appropriately if necessary.
 2. On return visit bedwetters and parents will be given the option of using medication , no further treatment, or alarm therapy.
 3. If patients choose alarm therapy, they will be asked if they wish to participate in the Randomized study comparing GoGoband® vs SNEA.
 4. Alarms will be provided to the patients free of cost to participants
 5. Patients in the alarm group will be treated for 3 months continuously.
 6. Patients in the SNEA group will record nightly if they wet their clothes and the report will be recorded and reviewed weekly
 7. GoGoband® patients' data will be automatically saved on the HIPPA Compliant servers and subsequently reviewed at the end of the week.

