5.2 Outcome Variables

5.2.1 Primary Outcome Variables

Variables:

Wetting event: Dry or Wet

Did patient wear the device: yes or no used to measure compliance

Did patient take the medication: yes or no used to measure compliance

Is the patient considered cured (dry 29/30 nights) : yes or no

Is the patient partially better (improvement of 50% or more compared to pre treatment)

Does the patient show no improvement (<50% improvement compared to Pre treatment)

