3.2 Assessments

3.2.1 Efficacy

SNEA: Device Will be provided to the patient

1. A log will be kept document that the patient wore the device that night
2. Mark if they were wet or dry that morning
3. if the alarm sounded that night
4. whether the device was on the patient in the morning
5. A log will be kept if the patient took ibuprofen or any Ansaïd that day

GoGoband®: Device Will be provided to the patient

1. A log will be kept identifying that the patient wore the device that night
2. Mark if they were wet or dry that morning
3. if the alarm sounded that night
4. whether the device was on the patient in the morning
5. A log will be kept if the patient took ibuprofen or any ansaid that day

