3.2.5 Biomarkers (if applicable)

3.3 Study Procedures

3.3.1 Study Schedule

Total study time is 3 months exclusive of prestudy visit which should be within 2 months of start of study.

Prestudy entry:

- all Nocturnal enuresis patients are all evaluated with physical examination and post void residual check.
- DVQ questionnaire is administered
- Inclusion and exclusion criteria evaluated
- treated with standard urotherapy previously described.

Visit 1:

- Confirm that patient has no daytime voiding symptoms identifying patient has MNE and qualifies for study
- Offer the patient treatment Choices:

2000031281

February 20, 2024

- medical treatment if so no longer candidate for study
- Alarm therapy: If Alarm therapy is chosen: randomize into SNEA or GoGoband®
- Consent to be signed
- Dispense alarm that day or have patient return within a week to have the alarm demonstrated and how to setup and to take home.
- Subject log is given along with alarm.

Visit 2:

- 1 month virtual or in person to follow progress,
- log is handed in, scanned into my chart, faxed or emailed
- new log dispensed

Visit 3:

- 2 month virtual or in person to follow progress
- log is handed in, scanned into my chart, faxed or emailed
- a new log dispensed

Visit 4:

- 3 months virtual or in person to close out study,
- log is handed in, scanned into my chart, faxed or emailed.
- Patients are informed that they can keep the alarm and continue to use it if they wish.

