3.4.3 Planned Analysis

3.4.3.1 Primary Analyses

Outcomes will be evaluated between the 2 groups using crosstab analysis of the data for the following data :

Wetting event: Dry or Wet

Did patient wear the device: yes or no used to measure compliance

Did patient take the medication: yes or no used to measure compliance
 Is the patient considered cured (dry 29/30 nights) : yes or no
 Is the patient partially better (improvement of 50% or more compared to pretreatment)
 Does the patient show no improvement (<50% improvement compared to Pretreatment)
 Logistic regression analysis may be performed on the incremental wet dry data vs time to achieving dryness

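### The two 50%-improvement outcomes depend on a pre-treatment wet-night rate with no stated source or date and no prospective record; a short log before randomisation would supply it.

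*Combined protocol and SAP*

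**What the plan says.** Section 5.2.1 (Primary Outcome Variables) lists "Is the patient partially better (improvement of 50% or more compared to pre treatment" and "Does the patient show no improvement (<50% improvement compared to Pre treatment". The Synopsis lists the same two categories. Section 3.4.3.1 (Primary Analyses) compares them between arms by crosstab, again as "Is the patient partially better (improvement of 50% or more compared to pretreatment". None of these places defines the reference rate by source, time window or date.

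On timing, section 5.1 states that "All patients to be evaluated for nocturnal enuresis will undergo standard evaluation and initial treatment", and it places the choice of alarm therapy at the return visit. Section 3.3.1 (Study Schedule) has children "treated with standard urotherapy previously described" at prestudy entry and refers to a "prestudy visit which should be within 2 months of start of study". At Visit 1, in the same section, "Subject log is given along with alarm".

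On content, the log items in section 3.2.1 (Efficacy) concern nights with a device: whether it was worn, whether the alarm sounded, whether it was still on in the morning, and "Mark if they were wet or dry that morning". No run-in diary appears in the schedule, the visit list (3.3.5) or Data Collection (4.5). The only wetting frequency mentioned before the alarm is the entry threshold of 2 wet nights a week in section 5.3, with no stated source. The subject characteristics in 3.4.3.4 are age, sex and DVQ scores, without a baseline wetting rate.

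**The concern.** A percentage improvement needs a denominator. Here the numerator is a nightly record (a family log, or server data for GoGoband®), while the denominator has no prospective source. If it is a reported frequency, two kinds of measurement are being compared, and error in the report moves children across the 50% line.

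The date of the denominator is also open. Urotherapy is described as treatment and comes before the alarm, so two analysts following the text could use different reference rates and class the same child differently. At stake is the meaning of the partial-response and no-improvement categories, and the chance to use baseline wetting as a covariate.

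**Working it through.** **1. The plan's own figure.** Section 3.4.2 gives 29 for 0.5 versus 0.8, one-sided 5%, power 0.8. The unpooled formula gives [0.5×0.5 + 0.8×0.2] × ((1.645 + 0.842)/0.3)² = 0.41 × 68.7 = 28.16, rounded up to 29 per arm. This reproduces. The section does not say which outcome the two proportions describe, so the present point does not change the figure.

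**2. The classification rule.** Let b be the child's true rate just before the alarm and r the reference rate actually used. A child counts as improved when the on-alarm rate is at most 0.5r. The true reduction needed is therefore 1 − 0.5r/b, which equals 50% only when r = b.

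**3. Which date (urotherapy effect u assumed; the documents give none).** If r is the rate before urotherapy, b = r(1 − u) and the reduction needed on the alarm is 1 − 0.5/(1 − u):

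| u | Reduction needed on the alarm |
|---|---|
| 0% | 50% |
| 10% | 44% |
| 20% | 37.5% |
| 30% | 29% |
| 40% | 17% |

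Take an invented child with 5 wet nights a week before urotherapy, 4 after it and 2.4 on the alarm. Against 5, improvement is 1 − 2.4/5 = 52%. Against 4, it is 1 − 2.4/4 = 40%. The same child is partially better on one reading and not improved on the other.

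**4. Effect on the contrast.** Assume beta-distributed reductions (concentration 3) and u = 20%, with the reference taken before urotherapy:

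| Responders, reference after urotherapy | Responders, reference before urotherapy | Difference |
|---|---|---|
| 50% vs 80% | 66% vs 89% | 30 → about 24 points |
| 25% vs 50% | 39% vs 66% | 25 → about 27 points |
| 20% vs 50% | 33% vs 66% | 30 → about 33 points |

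Response rises in both arms, but the contrast may narrow or widen. In the first row, one-sided power at 50 per arm goes from 0.94 to 0.89.

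**5. Recall error for one child (1 night a week assumed).** From step 2, a true rate of 2 a week recalled as 3 needs a 25% reduction (1 − 0.5×3/2); recalled as 1, it needs 75%. At 4 a week the range is 37.5% to 62.5%. At 6.2 a week, the mean before treatment in the uncontrolled series in section 2.1.2, it is 42% to 58%.

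**6. Recall error across children (simulation).** The residual wet fraction is assumed Beta(1.2, 1.2), with recall error normal and unbiased:

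| Recall SD (nights/week) | Misclassified, baseline even over 2–7 | Misclassified, baseline near 6.2 (SD 1), baseline and recall capped at 7 |
|---|---|---|
| 0.5 | about 6% | about 3% |
| 1 | about 11% | about 6% |
| 1.5 | 15–16% | about 8% |

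With the beta model of step 4 at 50% versus 80% and the even 2–7 baseline, a recall SD of 1 night reduces the difference from 30 to about 28 points and power at 50 per arm from 0.94 to 0.91. With baselines near 6.2, the difference stays at about 30 points.

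**The case against.** The strongest reply is that the randomised comparison is little harmed. Urotherapy comes before randomisation in both arms. The primary objective in the Synopsis is the dry-night rate. Neither that rate nor the cure outcome (dry 29 of 30 nights) uses a baseline. The loss of contrast from recall error is small. All of this stands and limits the weight of the point.

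A reader might also infer more than the documents support:

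- **That the reference is taken before urotherapy.** Visit 1 is the return visit after urotherapy, and a frequency taken there would post-date it. The documents do not say when it is taken.
- **That the entry threshold is not checked after urotherapy.** Staff confirm at Visit 1 that the child qualifies. The check is unspecified, not shown to be absent.
- **That a pre-urotherapy reference always shrinks the difference between arms, or favours GoGoband®.** Step 4 shows that the direction depends on the true responder rates, and urotherapy reaches both arms alike.
- **That recall differs by arm.** This could happen if the rate were asked for once the device was known, but the plan does not fix when it is asked.

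The alarm log and flowchart are listed as appendices without their content, so a baseline field on the log is possible. Since the log is issued with the alarm, such a field would still hold a recalled figure. Early GoGoband® training nights cannot serve instead: they are device nights and exist in one arm only.

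**Conclusion.** The point holds in a limited form. Two listed primary outcomes use a reference rate that is undefined in source and date, and the plan as written records no nights from which to derive it. That the rate would rest on recall is an inference from the absence of any described prospective source. The ambiguity over urotherapy is real on the text and can change a child's category.

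The sizes rest on assumptions the documents cannot settle: 6% to 16% misclassified with baselines spread over 2 to 7 nights a week, 3% to 8% with baselines near 6.2, and about 2 of 30 points of contrast at a recall SD of 1 night. The dry-night rate, the cure outcome and the sample size of 29 are untouched. The case for change is that a better measurement is cheap, and that a baseline not recorded before the alarm starts cannot be recovered prospectively.

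**What to change.** Define pre-treatment as the wet-night rate logged over a fixed period, for example 14 nights, after urotherapy has started and before randomisation, in both arms, using the wet/dry item of the existing log. Use that rate for the 50% rule, to document the entry criterion of 2 wet nights a week, and as a baseline covariate in the between-arm comparison.

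The cost is one extra log in an interval that already exists, with no added visit, though some logs will go to families who then choose another option. Consent is currently signed at Visit 1, so either consent for the log is obtained at the prestudy visit, or the log is issued as part of routine evaluation with IRB agreement. The schedule sets no minimum interval before Visit 1, so families with a shorter one would wait a few nights before randomisation. For children already enrolled, record the source and date of each pre-treatment rate.

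A lesser alternative is to define the reference as the frequency asked for at Visit 1 before randomisation. That settles the urotherapy ambiguity at almost no cost but leaves the recall error.

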3.3.2 Informed Consent

Informed consent will be obtained from all participants, including assents from appropriately aged minors.

3.3.3 Screening

Screening will be performed at the initial visit by members of the research staff with the use of the DVQ which will confirm a diagnosis of MNE or NMNE. Other exclusion questions will be ascertained on the initial visit as part of the usual evaluation

3.3.4 Enrollment

The person performing the initial screening and evaluation of the patient will be the person in charge of enrolling the patient

3.3.5 On Study Visits

Study visit 1: enrollment and study logs will be handed out along with alarms

Study visit 2: review of progress

review logs

Identify issues with compliance and correct them if possible

Identify any safety issues

Study visit 3: review of progress

review logs

Identify issues with compliance and correct them if possible
Identify any safety issues

Study visit 4: review of progress
review logs
Identify issues with compliance
Identify any safety issues
Close out study

3.3.6 End of Study and Follow-up

Patients who withdraw from the study due to lack of efficacy of the treatment will then be allowed to continue regular treatment options afforded to patients with MNE.

Patients that failed alarm therapy will be candidates to start treatment with desmopressin and if they fail that they can proceed to the addition of additional medications such as imipramine, atomoxetine, guanfacine or oxybutynin

3.3.7 Removal of subjects

Non-compliant patients will be removed from the study. Alarms will not be requested back from the participants.

Reasons for noncompliance will be the following

1. Not using device
2. Not filling in and submitting monthly logs.

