6.1.2 Device Administration and Schedule

SNEA: Device Will be provided to the patient

1. Instruction will be provided on how to set up the device and use it
2. The device will be worn consecutively for 3 months.
3. The alarm use will be terminated if they have been dry for 3 months consecutively.

GoGoband®: Device Will be provided to the patient

1. Instruction will be provided on how to set up the device and use it
2. The device will be worn consecutively for 3 months
3. The device will follow the built in algorithm in the device to decide when to begin the weaning process.
4. The weaning process will occur automatically until there no more nights in which the system will sound impending urination alarms

Non-compliant patients will be removed from the study. Alarms will not be requested back from the participants.

Reasons for noncompliance will be the following

1. Not taking medication
2. Not using device
3. Not filling in and submitting biweekly logs.

If a bedwetting alarm breaks or is nonfunctional the device will be replaced, and the study will proceed from the last active day

Method of Assignment/Randomization (if applicable)

2000031281

February 20, 2024

Randomization will be accomplished by having 100 envelopes with 50 SNEA and 50 GoGoband® choices. The envelopes will be distributed to the sites and pulled randomly at each site.

Age matching:

After 50% enrollment in any group the average age and standard deviation of the group will be calculated and an effort to adjust enrollment so groups are age matched will be made.

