3.4.3.3 Safety

The likelihood of safety issues is minimal with bedwetting alarms. Any major safety events will be reported. Also patients who drop out due to excess startling or unwillingness to continue to wear the alarm will be considered failures and included as such in the data analysis.

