3.4.3.7 Other

3.4.4 Subsets and Covariates

3.4.5 Handling of Missing Data

Patients who drop out of the study will be considered failures for purposes of the study with regards to success vs partial or failure analysis
 Dry /wet night rates will be maintained for the overall analysis of overall dry/wet ratios regardless of the patient ceases participation

4 Trial Administration

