4.6 Data Quality Assurance

Data quality consists of data logs which need to be maintained by the patients. Other than reminding patients that the data needs to be entered we are constrained by lack of being able to record events if the patient does not. The GoGoband® system has a built in system of recording wet dry events therefore this data will be available consistently as long as the patients use the device.

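### A child who stops wearing the alarm because dry is removed for non-use, and can then be scored a failure or lost from the cure comparison

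*Combined protocol and SAP*

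**What the plan says.** - **Removal.** Section 3.3.7: "Non-compliant patients will be removed from the study. Alarms will not be requested back from the participants". The grounds listed are not using the device and not submitting logs. Section 6.1.2 has the same rule for both arms. Neither gives a threshold or a reason qualifier for non-use.
- **Drop-outs.** Section 3.4.5: "Patients who drop out of the study will be considered failures for purposes of the study with regards to success vs partial or failure analysis". Section 3.4.3.3 adds that "patients who drop out due to excess startling or unwillingness to continue to wear the alarm will be considered failures".
- **Nightly data.** Section 3.4.5 also says: "Dry /wet night rates will be maintained for the overall analysis of overall dry/wet ratios regardless of the patient ceases participation".
- **Stopping for dryness.** The only such rule is in section 6.1.2, for the standard alarm (SNEA): "The alarm use will be terminated if they have been dry for 3 months consecutively". For GoGoband, weaning silences the alarms, but the device is still to be worn for 3 months.
- **Cure.** Section 5.2.1 lists among the primary outcome variables: "Is the patient considered cured (dry 29/30 nights) : yes or no". It also lists partial and no improvement. No section says which 30 nights count.
- **Visits and records.** At visits 2 and 3 the staff are to "Identify issues with compliance and correct them if possible" (section 3.3.5). Of the automatic GoGoband record, section 4.6 says that "this data will be available consistently as long as the patients use the device". Section 3.2.1 has families in both arms log wear and morning wet/dry status as separate items.

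**The concern.** Stopping the alarm because it has worked is a foreseeable event in an alarm trial. The background (section 2.1.1) itself describes GoGoband children as cured after weaning plus one dry week, in a process that may take only days. The rules treat such a child like one who abandoned the device. The child is removed, and the plan leaves open whether that means a failure or an absence from the comparison. That choice could then be made after results are seen.

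At stake is the cured/partial/no-improvement comparison. If stopping for dryness is equally common in both arms, the cost is some power. If it differs, the comparison is biased: against GoGoband when more GoGoband children stop, in its favour when more SNEA children stop.

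**Working it through.** **Reading the rules together**

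1. A child stops wearing the alarm because dry. Visits 2 and 3 may reverse this. If they do not, sections 3.3.7 and 6.1.2 remove the child.
2. The SNEA stopping rule does not help. It needs 3 consecutive dry months, and each child is in the study for 90 days (section 5.1.1), so it cannot operate before the study ends. GoGoband has no such rule.
3. After removal the child is either a failure (if removal counts as dropping out) or missing from the comparison. The text does not decide.
4. The unnamed window matters. If any 30 nights count, a cure already reached can be cancelled. If the last 30 count (nights 61 to 90), a child who stops before night 61 has no alarm nights in the window, the GoGoband automatic record there is empty, and removal, on its natural reading, ends the log that could show dryness.
5. The dry-night ratio is less exposed: nights already recorded are kept, so only later nights are lost.

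**The plan's own figure**

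Section 3.4.2 gives 29 for 0.5 vs 0.8, one-sided 5%, power 0.80. The unpooled formula reproduces it per group: (0.25 + 0.16) × ((1.645 + 0.842)/0.3)² = 28.16, rounded up to 29. Section 5.3.1 plans 50 per arm.

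**Illustration of size**

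Inputs from the plan: n = 50 per arm, one-sided 5%, rates p = 0.8 (GoGoband) and 0.5 (SNEA). Two assumptions: these are cure rates (section 3.4.2 does not name the outcome), and a share s of successes stops because dry (no value is given).

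- Children affected at s = 10% to 20%: 50 × 0.8 × s = 4 to 8 of 40 GoGoband successes; 50 × 0.5 × s = 2.5 to 5 of 25 SNEA successes.
- Scored as failures: observed rate p(1 − s), n = 50.
- Excluded: observed rate p(1 − s)/(1 − ps), n = 50(1 − ps).
- Power = Φ[(difference − 1.645 × SE pooled)/SE unpooled].

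No rescoring: (0.30 − 1.645 × 0.0954)/0.0906 = 1.58, power 94.3%. With s = 10% in both arms, scored as failures (0.72 vs 0.45): (0.27 − 1.645 × 0.0985)/0.0948 = 1.14, power 87.3%. The other rows follow in the same way.

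| Share stopping, GoGoband / SNEA | True rates | Quantity | Failures | Excluded |
|---|---|---|---|---|
| 2% / 2% | 0.8 / 0.5 | power | 93.1% | 94.2% |
| 5% / 5% | 0.8 / 0.5 | power | 91.1% | 94.0% |
| 10% / 10% | 0.8 / 0.5 | power | 87.3% | 93.6% |
| 15% / 15% | 0.8 / 0.5 | power | 82.9% | 93.2% |
| 20% / 20% | 0.8 / 0.5 | power | 78.2% | 92.8% |
| 15% / 10% | 0.8 / 0.5 | power | 75.6% | 91.5% |
| 20% / 10% | 0.8 / 0.5 | power | 60.6% | 88.7% |
| equal shares | 0.5 / 0.5 | false positives | 5.0% | 5.0% |
| 10% / 15% | 0.5 / 0.5 | false positives | 8.2% | 6.6% |
| 10% / 20% | 0.5 / 0.5 | false positives | 12.7% | 8.6% |
| 15% / 10% | 0.5 / 0.5 | false positives | 2.9% | 3.7% |
| 20% / 10% | 0.5 / 0.5 | false positives | 1.6% | 2.7% |

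With equal shares under failure scoring, power drops below the planned 80% only above s of about 18%. Using the unpooled variance throughout changes these figures by at most 1.7 points.

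**The case against.** Families are told to wear the device for the full 3 months and must be willing to adhere, weaning keeps the device on, and staff correct non-use, so stopping because dry may be rare. The plan gives no threshold for non-use and treats wear as a nightly compliance variable, so a few unworn nights need not lead to removal. The failure rule sits under missing data; a child already dry on 29 of 30 nights has an observed result, so nothing needs imputing. The Synopsis objective is the dry-night rate, whose recorded nights are kept. Power loss and false-positive inflation need opposite directions of imbalance and cannot both occur. Fifty per arm against a calculated 29 gives slack.

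Much of this stands as a limit on size. At shares of 2% to 5% the effect is small, more stopping on GoGoband lowers the false-positive rate, and nothing in the documents supports more stopping on SNEA. It does not remove the problem. The missing-data reading is only one of those the text allows, correction is asked for only where possible, and no section exempts the dry child or says what removal means for scoring. Cure and partial improvement remain listed primary outcome variables.

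**Conclusion.** The concern holds and should be fixed. Followed as written, the removal and drop-out rules can turn a success into a failure or drop it from a listed primary comparison. The size is unknown because the documents give no frequency. On the assumed equal shares of 10% to 20%, power falls from 94% to between 87% and 78% under failure scoring, costs under 2 points under exclusion, and the false-positive rate is unchanged. Only a difference between arms does more: at 10 points apart, power of 61% (failures) or 89% (excluded) if GoGoband children stop more, or a false-positive rate of 12.7% or 8.6% if SNEA children stop more. These figures also assume that 0.8 and 0.5 are cure rates. Confidence is medium, because the rules are clear on the page but the frequency is not.

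**What to change.** Amend sections 3.3.7, 3.4.5 and 6.1.2, and the matching sentence in 3.4.3.3:

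1. Stopping the device, or meeting either ground in 3.3.7, ends device use only. Every randomised child stays in follow-up and is analysed in the assigned arm.
2. Name the 30-night window once for both arms. Nights 61 to 90 are suggested, because they also count relapse after stopping; any 30 consecutive nights is the alternative.
3. A child who stops because dry keeps the morning wet/dry log to day 90, gets a reason code for this, and is scored on that window like everyone else.
4. Score as failures those who stop for any other reason, and those who stop because dry but whose log does not cover the window (for example, fewer than 29 of 30 nights marked, with an unmarked night counted as not dry).
5. Report by arm how many stopped because dry and how many of these lacked a covering log.

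The 3-month wear instruction stays. The cost is wording, one reason code and an approved IRB amendment (section 4.2); the log already exists in both arms. Families must keep logging after stopping, GoGoband nights after stopping rest on the log alone, and a dry child who gives up both alarm and log is still a failure, though by a stated rule and counted by arm.
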